6.3 Safety Assessments

6.3.1 *Adverse Events*

AEs will be followed, recorded, and reported in line with the procedures described in [Section 8](#).

6.3.2 *Clinical Laboratory Evaluations*

All laboratory samples will be processed and shipped to the central laboratory, as described in the Laboratory Manual. The central laboratory will analyze the samples or send them to reference laboratory(ies) for analysis, as indicated in the manual. Refer to the central Laboratory Manual for the maximum total volume of blood to be collected per patient throughout the study.

Non-fasting blood and urine samples will be collected at the times indicated in Table 1. On dosing day(s) sampling for the analysis of clinical laboratory parameters will be performed before the administration of study medication.

The following parameters will be assessed:

Hematology: hemoglobin, hematocrit, red blood cell (RBC) count, RBC morphology, platelets, total WBC count, differential WBC count, lymphocyte count, and ANC

Biochemistry: albumin, alkaline phosphatase, ALT, amylase, AST, blood urea nitrogen, bicarbonate, calcium, chloride, creatine phosphokinase (CPK), creatinine, phosphorus, gamma glutamyltransferase (GGT), glucose, lactate dehydrogenase (LDH), lipase, LDL-C, HDL-C, potassium, sodium, total and direct bilirubin, TC, and triglycerides (TG)

Urinalysis: pH, specific gravity, creatinine, glucose, bilirubin, blood, and protein

Screening serology tests will be performed to assess HIV (antibody), hepatitis C (antibody), hepatitis B surface antigen, or hepatitis B core antigen antibody. For hepatitis B, the following tests will be done at the Screening Visit and patients with a positive result for either hepatitis B surface antigen and or hepatitis B core antigen antibody will be excluded from the study.

Serum (β -human chorionic gonadotrophin) pregnancy testing will be performed at the Screening Visit, and urine pregnancy tests will be performed at the other study visits in the Treatment Period.

Refer to the Laboratory Manual for details regarding the collection, processing, and shipping of the blood and urine samples.

The investigator must review the laboratory report, document this review, and record any clinically relevant changes occurring during the study in the AE section of the eCRF. Whenever possible, the underlying cause for clinically relevant laboratory value should be recorded as an AE, rather than the laboratory value itself. The laboratory reports must be filed with the source documents. Clinically significant abnormal laboratory findings are those that are not associated with the underlying disease, unless judged by the investigator to be more severe than expected for the patient's condition.

All laboratory tests with values considered clinically significantly abnormal during the patient's participation in the study or within 2 weeks after the last dose of study medication should be repeated until the values return to normal, or baseline, or are no longer considered clinically significant by the investigator or medical monitor.

If such values do not return to normal/baseline within a period of time judged reasonable by the investigator, then the etiology should be identified, and the sponsor notified.

6.3.2.1 Potential Drug-induced Liver Injury

Hy's Law cases have the following 3 components:

1. The drug causes hepatocellular injury, generally shown by a higher incidence of ≥ 3 -fold elevations above the ULN of ALT or AST than the placebo
2. Among study patients showing such aminotransferase elevations, often with aminotransferases much greater than $3 \times \text{ULN}$, one or more also shows elevation of serum total bilirubin to $> 2 \times \text{ULN}$ or INR > 1.5 , without initial findings of cholestasis (elevated ALP)
3. No other reason can be found to explain the combination of increased aminotransferase and total bilirubin, such as viral hepatitis A, B, or C; evidence for biliary obstruction; acute alcoholic hepatitis (recent drinking and AST $> 2 \times \text{ALT}$ are supportive); recent history of severe hypotension or congestive heart failure; other underlying viral disease; pre-existing or acute liver disease; or another drug (including non-prescription products such as herbal supplements) capable of causing the observed injury

During the study, the investigator will remain vigilant for increases in liver biochemistry. The investigator is responsible for determining whether a patient meets potential drug-induced liver injury criteria at any point during the study.

In the event that a patient shows laboratory results of:

- AST or ALT: $> 5 \times \text{ULN}$ persisting for 2 weeks after study medication interruption or second occurrence of $> 5 \times \text{ULN}$
- $\geq 3 \times \text{ULN}$ and (total bilirubin $\geq 2 \times \text{ULN}$ or INR > 1.5)
- $\geq 3 \times \text{ULN}$ with appearance of fatigue, nausea, vomiting, right upper quadrant pain or tenderness, fever, rash and/or eosinophilia ($> 5\%$)

Please refer to [Appendix 4](#) for further information.

6.3.3 Pregnancy

WOCBP includes any female who has experienced menarche and who has not undergone successful surgical sterilization (e.g., hysterectomy, bilateral tubal ligation, or bilateral oophorectomy) or is not postmenopausal. Postmenopausal is defined as ≥ 12 months with no menses without an alternative medical cause. WOCBP must have a negative serum pregnancy test at screening and a negative urine pregnancy test on Day 1 prior to randomization.

Serum (β -human chorionic gonadotrophin) or urine pregnancy tests will be performed for WOCBP at the Screening Visit. Urine pregnancy tests will be performed at each study visit.

Serum pregnancy test results must be negative and must be available before Day 1. A pregnancy test must be performed at each study visit, and the result must be negative for the patient to continue to be eligible. If the test result is positive, the patient must be excluded from the study (if at the Screening Visit) or discontinued from the study (if at subsequent study visits). The serum pregnancy tests will be analyzed by the central laboratory; urine pregnancy tests will be analyzed locally.

Male patients will be required to inform the investigator if their partner becomes pregnant during the study.

The investigator should inform the sponsor within 24 hours of learning of the pregnancy or partner pregnancy by completing and submitting a pregnancy report form to the ProPharma Group, as shown in **SERIOUS ADVERSE EVENT CONTACT INFORMATION**.

If a patient becomes pregnant, she will not receive any further study medication. The investigator will record pregnancy information on the appropriate form and submit it to the sponsor within 24 hours of learning of the partner's pregnancy. Any pregnant patient or pregnant partner of a male patient and the fetus will be closely followed up throughout the duration of the pregnancy to determine the outcome (including spontaneous miscarriage, elective termination, normal birth, or congenital abnormality). The investigator will ask the patient to provide informed consent to record information on the health of the baby. Information on the status of the mother and child will be forwarded to the sponsor. Generally, follow-up will be required for no longer than 6 to 8 weeks beyond the estimated delivery date. Any termination of the pregnancy will be reported regardless of fetal status (presence or absence of anomalies) or indication for the procedure.

While pregnancy itself is not considered to be an AE or SAE, any pregnancy complication or elective termination of a pregnancy for medical reasons will be reported as an AE or SAE. Abnormal pregnancy outcomes (e.g., spontaneous abortion, fetal death, stillbirth, congenital abnormalities, ectopic pregnancy) will be considered SAEs.

6.3.4 12-lead Electrocardiogram

Triplet 12-lead ECGs will be obtained as outlined in **Table 1** using an ECG machine that automatically calculates the heart rate and measures PR, QRS, QT, and QTc intervals. At each time point at which triplicate ECG are required, 3 individual ECG tracings should be obtained as closely as possible in succession, but no more than 2 minutes apart. The full set of triplicates should be completed in less than 4 minutes.

The ECG tracing should include the date and time of the assessment and the signature of the person who made the interpretation; the tracing will be archived at the study site.

6.3.5 *Vital Signs*

Vital signs will be measured in a semi-supine position after 5 minutes of rest and will include temperature, systolic and diastolic blood pressure, pulse, and respiratory rate.

6.3.6 *Physical Examination*

Physical examinations will be performed by a Doctor of Medicine (MD) or equivalent, or someone who is authorized to perform the examinations by training and has been delegated this task by the investigator.

A full examination will be performed at the Screening Visit. A full examination will include general appearance, skin, head, eyes, ears, nose, throat, neck, thyroid, chest/lungs, heart, abdomen, lymph nodes, and extremities.

An abbreviated examination will be performed at the Day 1 and Day28/ET Visits and will include symptom-focused assessments. An abbreviated examination does not preclude examination of any of the other body systems as clinically indicated. Every effort should be made to ensure the same evaluator will complete the examination for each participant at all visits throughout the study. Documentation of who performed the examination is to be recorded in the patient source documentation.

Height will be measured and recorded at the Screening Visit, and weight will be measured and recorded at each study visit. The patient should be dressed in light clothing, without shoes.

6.4 *Pharmacokinetics*

The PK of ATI-1777 will be preliminarily evaluated by measurement of ATI-1777 concentrations in plasma samples obtained using a sparse sampling schedule. A sparse sampling approach is being employed because it is not anticipated that clinically relevant plasma concentrations will be observed.

Actual time of PK sample collection, the time of last application of study medication, and the volume of study medication applied in the last study medication application must be collected in the eCRF.

A total of 8 PK samples will be collected from each patient.

One sample will be collected before study medication application and 1 sample will be collected approximately 2 hours after application on each of Days 1, 8, and 15.

Samples for Day 28 will be collected from 3 subgroups of patients within each of the specified time windows as follows:

- Subgroup 1: One sample predose and one sample at 0.5 to 2.5 hours post application

- Subgroup 2: One sample at 2.5 to 5 hours post application and one sample at least 2 hours later
- Subgroup 3: One sample at 5 to 8 hours post application and one sample at least 2 hours later (prior to the subsequent application)

The IXRS system will be used to randomly assign patients to subgroups.

The plasma samples will be analyzed for ATI-1777 using a validated assay. Samples will be used to evaluate the PK of ATI-1777. Each plasma sample will be divided into 2 aliquots (1 each for PK and a backup).

Detailed instructions for the PK blood collection, labeling, processing, storage, and shipping will be provided to the site in the Laboratory Manual.

7 TREATMENTS

7.1 Investigational Product(s)

7.1.1 *Description of Study Medications*

Test Product

Name: ATI-1777
Dose(s): Up to 8 mL 2% w/w topical solution applied to affected skin areas
Mode of administration: Topical application to AD-affected skin areas
Manufacturer: *Drug Substance:*
GVK Biosciences Pvt. Ltd
Hyderabad, India

Drug Product:

Tergus Pharma
Durham, North Carolina, USA

Vehicle

Substance: Topical vehicle solution identical in appearance to ATI-1777
Dose(s): Up to 8 mL topical solution applied to affected skin areas
Mode of administration: Topical application to AD-affected skin areas
Manufacturer: Tergus Pharma
Durham, North Carolina, USA

7.1.2 *Preparation, Handling, and Storage*

The investigator (or designee) is responsible for the safe and proper storage of study medication at the site. ATI-1777 topical solution and vehicle topical solution will be stored under controlled conditions according to the storage requirements described on the label(s). ATI-1777 topical solution and vehicle topical solution should be stored at room temperature 15°C – 25°C (59°F – 77°F), with excursions permitted up to 30°C (86°F). The investigator (or designee) will instruct the patients to store the study medication in accordance to the instructions on the label.

7.1.3 *Packaging, Labeling, and Shipment*

ATI-1777 topical solution and vehicle topical solution will be packaged and labeled in accordance with all applicable regulatory requirements and Good Manufacturing Practice guidelines.

Fifty mL of ATI-1777 topical solution or vehicle topical solution will be provided in 60-mL amber glass bottles with 1-mL droppers metered to 0.25 mL.

ATI-1777 topical solution and vehicle topical solution will be shipped and stored under controlled conditions according to the storage requirements.

Refer to the Pharmacy Manual for full details for packaging, labeling, and shipment of the study medication.

7.2 Blinding

The study is double-blinded; therefore, the sponsor, investigators, study personnel, and the study patients will remain blinded to treatment allocation.

ATI-1777 and vehicle will be coded and labeled in a manner that protects blinding. The IXRS will permit rapid identification of the product (in case of medical emergencies), that does not permit detectable breaking of the blind.

Breaking of the blind is only allowed in the case of an emergency, when knowledge of the study medication is essential for the clinical management of the patient. The investigator must make every effort to contact the sponsor's medical monitor prior to breaking the blind and must contact the sponsor within 1 business day after the event, without revealing to the sponsor (or designee) the results of the code break, except to the ProPharma Group safety team. Patients whose treatment assignments are unblinded will not receive any further study medication.

Emergency unblinding will be organized through the IXRS. The investigator must record the date of unblinding and the reason. All breaks of the blind must be adequately documented in the patient's source documentation.

If an SAE is reported, the designated global patient safety representative may unblind the treatment assignment for the individual patient through IXRS in order to meet regulatory reporting requirements.

7.3 Method of Assigning Treatment

Each patient will be assigned a unique Patient Number, which will be obtained from the IXRS following the patient providing informed consent. The investigator will keep a record (the screening log) of patients who enter screening.

Randomization will be performed via a centralized IXRS. On Day 1, eligible patients will be assigned to ATI-1777 or vehicle in a 1:1 ratio. Patients will be allocated to treatment according to the randomization code.

If a patient withdraws from study participation, his/her unique identification number(s) cannot be re-used for another patient.

Patients will be stratified at randomization by severity of AD (moderate versus severe).

7.4 Dose and Administration

Patients will be instructed to apply a thin film of study medication, twice daily, once in the morning and approximately 8 to 12 hours later, to the identified target AD areas. Study medication should be applied using the metered dropper to drop study medication onto the skin and gently rubbing in over the target area. No more than a total of 8 mL of study medication should be applied to all combined target areas at a given administration session. Study medication should be applied to clean dry skin. The patient must wash her/his hands thoroughly before and after each study medication administration.

Investigational site staff will dispense study medication to the patient on Day 1. Subsequent study medication dispensing will be determined by the site based on the amount used between visits. Study medication bottles will be weighed by the site staff at the time of dispensing and when the bottles are returned. Patients are to return used and unused study medication bottles at each study visit so that the bottles can be weighed. Sites can re-dispense partially used bottles of study medication.

Patients will be trained by site staff on the appropriate application of study medication before the first application on Day 1, and the first application will be supervised by site staff. Patients may be retrained after Day 1 if site staff determines that it is necessary. Throughout the study, patients will record the amount applied in a patient diary.

Additional details on the application of study medication are in [Appendix 2](#) and the Pharmacy Manual.

7.4.1 *Identification of Target Treatment Areas*

On Day 1, the investigator will identify a target treatment area(s) that meets all inclusion criteria (e.g., a diagnosis of AD based on the criteria of Hanifin and Rajka ([Hanifin and Rajka 1980](#); [Appendix 3](#)), BSA between 3% and 20%, inclusive, and an IGA score of 3 or 4). The target treatment area cannot include the head (neck, scalp, face), palms of hands, soles of feet, groin, or genitalia. The investigator will record the identified target treatment area(s) on the body map in the patient's source documents and give to the patient to take home for reference. Up to 2 target treatment areas will be photographed at each specified protocol time point (see Table 1). Sites will use colored stickers to mark the treatment areas prior to the photographs being taken.

Patients will continue treatment of all target areas identified on Day 1, even if the lesion(s) have cleared. If new areas of AD develop while the patient is on study, study medication may be applied to these areas. New areas should be treated at the first sign of disease and continue until the Day 28 visit. New areas of treatment will be recorded in the source notes at the time the patient begins treating them with study medication.

7.4.2 Dose Modification

Study medication dosing for individual patients will be allowed to be paused and restarted if it is deemed to be in the best interest of the patient's safety due to AE. Decisions regarding dose interruptions or modifications will be made by the investigator in consultation with the medical monitor based on the clinical evaluation of the patient. All treatment interruptions and the reason for the interruption should be recorded in the eCRF.

Treatment with ATI-1777 should be temporarily interrupted in the event of severe AEs considered related to ATI-1777, or in the event of one or more of the abnormal laboratory values in Table 5.

Table 5 Study Medication Interruption Criteria

Laboratory Test	Hold Study Medication if:	Resume Study Medication if:
WBC count	$<2 \times 10^9/L$	$\geq 2.5 \times 10^9/L$
ANC	$<1 \times 10^9/L$	$\geq 1.5 \times 10^9/L$
Lymphocyte count	$<0.5 \times 10^9/L$	$\geq 0.75 \times 10^9/L$
Platelet count	$<75 \times 10^9/L$	$\geq 100 \times 10^9/L$
Hemoglobin	8 g/dL or a decrease >2 g/dL	≥ 10 g/dL
AST or ALT	$>3 \times ULN$	$<2 \times ULN$ or within 20% of baseline values
Serum creatinine	$>2 \times ULN$	$<1.5 \times ULN$ or within 10% of baseline value

ALT = alanine aminotransferase; ANC = absolute neutrophil count; AST = aspartate aminotransferase; ULN = upper limit of normal range; WBC = white blood cell

If a patient has one or more of the abnormal laboratory values noted in [Table 5](#), the investigator or designee upon receipt and review of the central laboratory report should instruct the patient to hold study medication applications. The investigator or designee should ask the patient about symptoms, concomitant illnesses and medications and repeat the test(s) as soon as possible. The medical monitor must be notified of dose interruptions due to AEs or laboratory abnormalities noted in Table 5.

If the retest confirms the abnormal laboratory value, then the study medication should continue to be held followed by repeat testing once a week or sooner at the discretion of the investigator. The patient should be followed until the laboratory abnormality(s) returns to normal or to baseline values.

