1.3.2.5 Cytopenias

Cytopenias (lymphopenia, neutropenia, anemia, and thrombocytopenia) have been reported after chronic oral dosing with commercially available JAK1/JAK2 and pan-JAK inhibitors such as ruxolitinib, upadacitinib, and tofacitinib. Treatment with ATI-1777 should be avoided in patients with cytopenias. Patients with laboratory values indicative of cytopenias will be excluded from the study. Cytopenias will be monitored during the study and reported as AEs.

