5.4 Premature Discontinuation

5.4.1 *Premature Discontinuation of Study Medication*

Patients should be permanently discontinued from study medication in the event of any of the following:

- The patient experiences significant worsening of AD such that additional therapy for the treatment of AD is required
- Confirmed, active infection with the SARS-CoV-2 virus
- Infection requiring parenteral antimicrobial therapy or hospitalization
- Symptomatic herpes zoster
- Malignancy – except for nonmelanoma skin cancer not in or near the treatment area
- Anaphylactic or severe allergic reaction
- WBC count: $<1 \times 10^9/L$ or second occurrence of $<2 \times 10^9/L$ – in each case, value should be confirmed by retesting before treatment discontinuation

- ANC: $<0.5 \times 10^9/L$ or second occurrence of $<1 \times 10^9/L$ – in each case, value should be confirmed by retesting before treatment discontinuation
- Lymphocyte count: $<0.3 \times 10^9/L$ or second occurrence of $<0.5 \times 10^9/L$ – in each case, value should be confirmed by retesting before treatment discontinuation
- Platelet count: $<50 \times 10^9/L$ or second occurrence of $<75 \times 10^9/L$ – in each case, value should be confirmed by retesting before treatment discontinuation
- Hemoglobin: $<6.5 \text{ g/dL}$ or second occurrence of $<8 \text{ g/dL}$ – in each case, value should be confirmed by retesting before treatment discontinuation
- AST or ALT:
 - $5 \times \text{ULN}$ persisting for 2 weeks of study medication interruption or second event of $>5 \times \text{ULN}$
 - $>3 \times \text{ULN}$ and (total bilirubin $>2 \times \text{ULN}$ or international normalized ratio [INR] of >1.5)
 - $3 \times \text{ULN}$ with total bilirubin $>2 \times \text{ULN}$ or symptoms of hepatocellular injury [fatigue, nausea, vomiting, right upper quadrant pain or tenderness, fever, rash and/or eosinophilia ($>5\%$)].
- Any patient who develops any of the following ECG findings during the active treatment phase will be instructed to stop study medication and will be withdrawn from the study:
 - Clinically significant rhythm disturbance other than sinus rhythm or ectopic supraventricular rhythm (ectopic atrial rhythm).
 - Clinically significant conduction disturbance including PR $>240 \text{ msec}$, pre-excitation (delta wave and PR $<120 \text{ msec}$), second degree or higher atrioventricular block.

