## 8.2. Stopping Rules

A patient will stop treatment with investigational agent if one or combination of the following occurs during the study:

- An infection which meets the criteria as a study medication-related serious adverse event (SAE)
- A deep venous thrombosis (DVT) and/or pulmonary embolism (PE)
- Lymphoma
- Hy's law ([Appendix 1](#))

Treatment with study medication should be temporarily interrupted in the event of severe AEs considered related to study medication, or in the event of one or more of the abnormal laboratory values in [Appendix 2](#).

[figure not shown]
The sponsor and ProPharma safety physician will meet regularly (every 4 weeks) and assess the ongoing safety of the study. Attention will be paid to the number of severe AEs and SAEs, with particular focus paid to the number of patients who meet individual patient stopping rules. PK data will be used in the assessment: events associated with high plasma levels will be considered of high significance.

If the study is stopped, a restart will not occur without agreement of the institutional review board (IRB) and the sponsor's medical monitor.

The study overview is specified in [Figure 1](#).

The schedule of study events is specified in Table 1.

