## Appendix 2 Study Medication Interruption Criteria

| Laboratory Test  | Hold Study Medication if:       | Resume Study Medication if:                               |
|------------------|---------------------------------|---|
| WBC count        | $< 2 \times 10^9/L$             | $\geq 2.5 \times 10^9/L$                                  |
| ANC              | $< 1 \times 10^9/L$             | $\geq 1.5 \times 10^9/L$                                  |
| Lymphocyte count | $< 0.5 \times 10^9/L$           | $\geq 0.75 \times 10^9/L$                                 |
| Platelet count   | $< 75 \times 10^9/L$            | $\geq 100 \times 10^9/L$                                  |
| Hemoglobin       | 8 g/dL or a decrease $> 2$ g/dL | $\geq 10$ g/dL  |
| AST or ALT       | $> 3 \times \text{ULN}$         | $< 2 \times \text{ULN}$ or within 20% of baseline values  |
| Serum creatinine | $> 2 \times \text{ULN}$         | $< 1.5 \times \text{ULN}$ or within 10% of baseline value |

ALT = alanine aminotransferase; ANC = absolute neutrophil count; AST = aspartate aminotransferase; ULN = upper limit of normal range; WBC = white blood cell

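### For baselines above 12 g/dL, the haemoglobin row of Table 5 lets the same value both require a hold and permit resumption

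*Protocol*

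**What the plan says.** Protocol section 7.4.2 sets out temporary interruption in Table 5, which has one column for holding and one for resuming.

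- **Hold, haemoglobin:** "8 g/dL or a decrease >2 g/dL". The reference value for the decrease is not given.
- **Resume, haemoglobin:** 10 g/dL or more, with no condition relative to baseline.
- **Other rows:** AST/ALT may also resume on a value "or within 20% of baseline values", and the creatinine row has a similar 10% alternative. WBC, ANC, lymphocytes and platelets use absolute limits in both columns.
- **Procedure below the table:** on a Table 5 value the investigator or designee "should instruct the patient to hold study medication applications", repeats the test and notifies the medical monitor. "If the retest confirms the abnormal laboratory value, then the study medication should continue to be held", with repeat tests weekly or sooner. The patient is followed until the value is normal or back at baseline.

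SAP Appendix 2 prints the same haemoglobin row ("8 g/dL or a decrease $> 2$ g/dL"; resume at 10 g/dL or more). SAP section 8.2 refers to it for interruption "or in the event of one or more of the abnormal laboratory values in" that appendix.

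The only other on-study haemoglobin limits are in Protocol section 5.4.1, for permanent discontinuation: below 6.5 g/dL, or a second value below 8 g/dL. Both are absolute.

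**The concern.** A hold rule and its resume rule should not both be satisfied by one value. In the haemoglobin row the hold can be triggered by a fall, while release depends only on the level reached. A patient who starts well above 10 g/dL can lose more than 2 g/dL and still be above 10, so the release condition is already met when the hold begins. The resume column then cannot say when that hold ends.

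What is at stake is consistent dosing safety across about 15 sites, not the efficacy inference. The trial is first-in-human. Protocol section 1.3.2.5 names anaemia among the class cytopenias and says "Cytopenias will be monitored during the study and reported as AEs". Cytopenias are also events of special interest in section 8.1.5. Two sites could handle the same result differently and both be following the table. Section 8.1.4 requires laboratory abnormalities that lead to interruption to be recorded as adverse events, so differences in holding could carry over into adverse event recording. That last step is inference, not something the documents state.

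**Working it through.** There is no power, alpha or sample-size figure to reproduce. The check is whether the two columns can be true at once.

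**Inputs.** Let b be baseline and h the on-study value, in g/dL.

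- Hold (Table 5): h at the 8 g/dL limit or lower, or b − h > 2. The table prints no comparison sign for the 8 and no reference for the decrease. Baseline is assumed as the reference because it is the one used in the AST/ALT and creatinine resume cells.
- Resume (Table 5): h ≥ 10.
- Entry floor (Protocol 5.2, exclusion 11): values below 8 are excluded. There is no upper limit.

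**Overlap.** The 8 g/dL part of the hold rule cannot meet h ≥ 10, so only the decrease matters:

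h ≥ 10 and h < b − 2, that is, 10 ≤ h < b − 2.

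This range is non-empty only if b − 2 > 10, so only if b > 12. Its width is b − 12. On a 0.1 g/dL grid:

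| Baseline | Values meeting both columns | Number | Decrease-triggering values ≥ 8.0 | Share |
|---|---|---|---|---|
| 12.0 | none | 0 | – | – |
| 13.0 | 10.0–10.9 | 10 | 30 (8.0–10.9) | 33% |
| 14.0 | 10.0–11.9 | 20 | 40 (8.0–11.9) | 50% |
| 15.0 | 10.0–12.9 | 30 | 50 (8.0–12.9) | 60% |

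The first baseline with an overlap on this grid is 12.1, at the single value 10.0. The shares count possible values, not patients.

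**Worked case.** b = 14.5, h = 12.0. The fall is 14.5 − 12.0 = 2.5 > 2, so hold. Also 12.0 ≥ 10, so the resume column is met. A retest of 12.0 again satisfies both.

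**Effective trigger.** The columns agree on a hold only when h < 10, that is, when the fall exceeds b − 10. This is more than 3, 4 and 5 g/dL at baselines 13, 14 and 15, against the stated trigger of 2.

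**Does another rule cover these values?** No. Every overlapping value is at least 10, and the section 5.4.1 limits are 6.5 and 8.

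**Other rows.** The hold and resume limits are separated for WBC (2 and 2.5), ANC (1 and 1.5), lymphocytes (0.5 and 0.75) and platelets (75 and 100), all × 10⁹/L. For AST/ALT, entry is capped at 2 × ULN, and 1.2 × 2 = 2.4 × ULN is below the hold limit of 3 × ULN. Creatinine could overlap only with a baseline above 2/1.1 ≈ 1.8 × ULN. Haemoglobin is the only row with a hold trigger based on a fall, and its resume cell does not refer back to that fall.

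**After the fix.** With resume defined as h ≥ 10 and b − h ≤ 2, no value meets both columns at any baseline from 8 to 18 g/dL, even when the first limit is read as ≤ 8.

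**The case against.** The strongest reply is that section 7.4.2 is a procedure, not just two columns. A confirmed abnormal value stays held, tests are repeated, the patient is followed to normal or baseline, and the medical monitor must be told. On that view the resume column applies only to later values. This helps on the day of the retest, but not afterwards. A later stable 12.0 from a baseline of 14.5 is still a fall of more than 2 g/dL and still at least 10. The sentence about normal or baseline governs follow-up. If it governed restart, the resume column would have no use.

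A second reply is that the decrease might be measured from the previous result. A stable 12.0 would then no longer be a fall, and resuming would conflict with nothing. The text does not exclude this, but it fits poorly with the retest step: a repeat test at the same level could not confirm a fall measured from the result just before it. Either way the missing reference needs to be supplied.

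Other points stand as limits on the importance of the issue:

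- Interruption decisions rest with the investigator in consultation with the medical monitor, and safety is also reviewed at the sentinel pause and every 4 weeks.
- The drug is topical with little or no systemic exposure expected. Scheduled on-treatment laboratory tests fall on Days 8, 15 and 28, so a resume decision arises mainly from the first two.
- Every overlapping value is above the entry floor of 8 g/dL.

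The proposed fix can also be criticised. Holding at more than 2 and resuming at 2 or less leaves no gap, so a change of 0.1 g/dL could switch dosing on or off. That is fair, and it is a reason to consider a tighter resume margin.

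**Conclusion.** The concern holds. As written, for any baseline above 12 g/dL, every haemoglobin value from 10 g/dL to just under baseline minus 2 both triggers a hold and meets the resume limit, in the protocol and in the SAP. The conflict covers the smallest falls that trigger a hold, and the range widens by 1 g/dL for each 1 g/dL of baseline above 12.

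The result assumes that the decrease is from baseline. With any other fixed earlier reference, the same overlap arises whenever that value exceeds 12 g/dL. The documents give no probability of such a fall, so the number of patients affected cannot be stated. Retesting and the medical monitor limit the harm, but the end of a decrease-triggered hold is left to case-by-case judgement although the table is meant to state it. Power, type I error and the primary analysis are untouched. It should be corrected because it is a dosing-safety rule in a first-in-human trial and the correction is small.

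**What to change.** In Protocol Table 5, state that the haemoglobin decrease is from baseline, and change the resume cell to require both at least 10 g/dL and a value no more than 2 g/dL below baseline. Copy the row to SAP Appendix 2. For baselines up to 12 g/dL nothing changes, because baseline minus 2 is then at most 10. At baselines 13, 14 and 15 the resume level becomes 11, 12 and 13 g/dL. If the medical monitor wants a gap between hold and resume, as in the blood-count rows, set a tighter margin below baseline.

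The cost is one table row in each document and no extra tests. Some holds will last longer. A patient who settles at 12.0 from a baseline of 14.5 could not restart, and with 28 days of treatment a hold from Day 15 could in effect end dosing. The sponsor should accept this knowingly.

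Two optional checks in the same edit:

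- Confirm that the 8 g/dL limit reads as below 8, in line with exclusion 11 and section 5.4.1. The missing sign may only be a text-extraction loss.
- Ask the medical monitor whether patients who entered with haemoglobin 8.0–9.9 g/dL or lymphocytes 0.50–0.74 × 10⁹/L may resume on return to baseline, since their resume limits (10 g/dL and 0.75 × 10⁹/L) lie above their entry values. A resume limit above the entry floor is defensible if intended.
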